### 5.5. Randomization and Masking

A randomization code for allocating subjects to each treatment group will be prepared by an unmasked biostatistician not connected with the study. Subjects will be then randomized 1:1:1:1 into 1 of 4 treatment arms at Visit 1:

- Nyxol in Stage 1; Nyxol + LDP in Stage 2
- Nyxol in Stage 1; Nyxol + LDP vehicle in Stage 2
- Placebo in Stage 1; Placebo + LDP in Stage 2
- Placebo in Stage 1; Placebo + LDP vehicle in Stage 2

Randomization will

The Treatment 1 (Nyxol/placebo) and Treatment 2 (LDP/LDP vehicle) study medications was masked to Investigators, Site Staff, study subjects, Ocuphire, and all other study personnel involved in the conduct of the study. Only in case of medical emergency or occurrence of SAEs will the randomization code be unmasked by the Medical Monitor and made available to the Investigator, Ocuphire, and/or other personnel involved in the monitoring or conduct of this study.

### 5.6. Analysis Variables

Variables to be summarized include demographics and baseline characteristics, medical (non-ocular) and ocular history, concomitant medications, and study drug accountability.

Efficacy variables include:

- Photopic and mesopic DCNVA (i.e., Near VA)
- Photopic and mesopic BCDVA (i.e., Distance VA)
- Photopic DCIVA (i.e., Intermediate VA)

- Photopic and mesopic PD
- Subject questionnaire responses related to change in near vision and satisfaction with near vision

Safety variables include:

- AEs
- Subjective ocular tolerability [REDACTED]
  - [REDACTED]
  - [REDACTED]
  - [REDACTED]
  - [REDACTED]
- IOP
- BCDVA
- Biomicroscopy
- Ophthalmoscopy
- Subject questionnaire
- Vital signs (HR and BP)
- Urine pregnancy tests for females of childbearing potential

## 6. SAMPLE SIZE

[REDACTED]

[REDACTED]

## **7. GENERAL CONSIDERATIONS**

### **7.1. Analysis Populations**

The following analysis populations will be defined for this study.

#### **7.1.1. Modified Intention-to-Treat (mITT)**

The mITT Population will include all randomized subjects who received at least 1 drop of Treatment 1 (Nyxol or placebo). The mITT Population will be used to analyze the primary endpoint as well as other efficacy endpoints, with subjects included in their randomized treatment regardless of the treatment they actually received.

#### **7.1.2. Per Protocol Stage 1 Population (PPS1)**

The PP Stage 1 (PPS1) Population will include all subjects in the mITT Population who receive 1 drop of Treatment 1 the day prior to Visit 2, have binocular DCNVA and BCDVA in photopic conditions at Baseline (Visit 1) and at 12 hours post-dose at Visit 2, and have no major protocol deviations considered to have significant impact on treatment outcome in Stage 1. The PPS1 Population will be used for analysis of select efficacy endpoints.

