#### 10.2. Analysis Populations

**Modified Intention-to-Treat Population:** The mITT Population will include all randomized subjects who received at least 1 drop of Treatment 1. The mITT Population will be used to analyze the primary endpoint as well as other efficacy endpoints.

**Per Protocol Stage 1 Population:** The PP Stage 1 (PPS1) Population will include all subjects in the mITT Population who receive 1 drop of Treatment 1 the day prior to Visit 2, have binocular DCNVA and BCDVA in photopic conditions at Baseline (Visit 1) and at 12 hours post-dose at Visit 2, and have no major protocol deviations considered to have significant impact on treatment outcome in Stage 1. The PPS1 Population will be used for analysis of select efficacy endpoints as specified in the SAP.

**Per Protocol Stage 2 Population:** The PP Stage 2 (PPS2) Population will include all subjects in the PPS1 Population who receive 1 drop of Treatment 1 the day prior to Visit 4, receive 1 drop of Treatment 2 at Visit 4, have binocular DCNVA and BCDVA in photopic conditions for at least 1 timepoint at Visit 4 after Treatment 2 dosing, and have no major protocol deviations considered to have significant impact on treatment outcome in Stage 2. The PPS2 Population will be used for analysis of select efficacy endpoints as specified in the SAP.

**All Randomized Population (ARP):** The ARP will include all randomized subjects. This population is also known as the Intention-to-Treat (ITT) Population. The ARP will be used in confirmatory efficacy analyses.

**Safety Population (SP):** The SP will include all randomized subjects who have received at least 1 drop of study treatment (Treatment 1 or Treatment 2). The SP will be used to summarize safety variables.

Per Protocol Populations include PPS1 and PPS2 throughout this document.

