#### **7.1.3. Per Protocol Stage 2 Population (PPS2)**

The PP Stage 2 (PPS2) Population will include all subjects in the mITT Population who receive 1 drop of Treatment 1 the day prior to Visit 4 and Visit 5, receive 1 drop of Treatment 2 (LDP or LDP vehicle) at Visit 4 and Visit 5, have binocular DCNVA and BCDVA in photopic conditions at the 30 Minute timepoint at Visit 5 (after Treatment 2 dosing), and have no major protocol deviations considered to have significant impact on treatment outcome in Stage 2. The PPS2 Population will be used for analysis of select efficacy endpoints.

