### 9.1. Clinical Efficacy

All efficacy data will be summarized by treatment group for the Baseline assessment; for Visit 1 (Stage 1 Day 1) post-treatment time points (0.5 hours, 1 hour, 3 hours, 5 hours, and 8 hours); Visit 2 (Stage 1 Day 8) time points (12 hour post-Treatment 1 dose, 12.5 hours, 13 hour, 15 hours, 17 hours, and 20 hours); Visit 3 (Stage 1 Day 10); Visit 4 (Stage 2 Day 1) time points (12 hour post-Treatment 1 dose, 0.5 hours, 1 hour, 3 hours, 5 hours, and 8 hours post-Treatment 2); and Visit 5 (Stage 2 Day 8) time points (12 hour post-Treatment 1 dose, 0.5 hours, 1 hour, 3 hours, 5 hours, and 8 hours post-Treatment 2).

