### 9.1.2. Secondary Efficacy Analyses

Secondary efficacy endpoints are indicated in Section 4.2.2. Secondary efficacy endpoints will be analyzed by study eye, fellow eye, and binocular (if available) using the the PPS1 and PPS2 populations, and the mITT population for selected endpoints (see the list of planned tables, Section 12.1, for details).

All continuous secondary endpoints derived from VA assessments, such as change in DCNVA, DCIVA, and BCDVA, will be analyzed using Early Treatment Diabetic Retinopathy Study (ETDRS) letters correctly read. Any secondary endpoints using Snellen measurements will be converted from letters read as follows:

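### The Per Protocol sets are fixed by the Visit 2 and Visit 5 conditions, so PP results at Visit 1, and at Visit 4 under the SAP's PPS2, drop validly measured subjects for later events

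*SAP*

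**What the plan says.** SAP 7.1.2 admits to PPS1 those mITT subjects "who receive 1 drop of Treatment 1 the day prior to Visit 2" who also "have binocular DCNVA and BCDVA in photopic conditions at Baseline (Visit 1) and at 12 hours post-dose at Visit 2" and have no excluding deviation in Stage 1. Protocol 10.2 defines PPS1 in the same way.

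SAP 7.1.3 requires for PPS2 that subjects take Treatment 1 the day before Visits 4 and 5, "receive 1 drop of Treatment 2 (LDP or LDP vehicle) at Visit 4 and Visit 5", and "have binocular DCNVA and BCDVA in photopic conditions at the 30 Minute timepoint at Visit 5". Protocol 10.2 asks for less. Its PPS2 is nested in PPS1 and needs dosing at Visit 4 only, and subjects must "have binocular DCNVA and BCDVA in photopic conditions for at least 1 timepoint at Visit 4 after Treatment 2 dosing".

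On use, SAP 9.1.2 says that secondary endpoints are analysed "using the the PPS1 and PPS2 populations, and the mITT population for selected endpoints", and refers to the table list in Section 12.1, which is blacked out. SAP 9.1 covers five post-dose times at Visit 1 and the full set of times at Visit 4. SAP 9.1.2 plans treatment comparisons at the Stage 1 and Stage 2 time points. No unredacted text defines a PP set specific to a visit.

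**The concern.** A per-protocol set is meant to remove data spoiled by poor adherence. Here sound Day 1 data are removed because of something that happened in the following week, after treatment had begun. That later event may be caused by treatment: protocol 5.9.1 lists adverse events and perceived lack of efficacy among the reasons for stopping. In the Phase 2 study (protocol 3.2), treatment-emergent events occurred in 34.1% of subjects on Nyxol + LDP against 4.4% on placebo alone, and one combination subject withdrew because of such events. Exclusion that differs by arm is therefore plausible, though not certain.

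At stake are the onset and first-day results: Nyxol alone at Visit 1, and the combination at Visit 4. In the PP sets these would describe only subjects who remained and were measured a week later.

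**Working it through.** **Which visit each set depends on**

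| Set | Latest condition for entry | Earlier visit affected |
|---|---|---|
| PPS1 (SAP and protocol) | Dose before Visit 2; 12-hour reading at Visit 2 | Visit 1 |
| PPS2 (SAP) | Dosing for Visit 5; 30-minute reading at Visit 5 | Visit 4 |
| PPS2 (protocol) | One post-dose reading at Visit 4 | None in Stage 2 |

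Under the protocol's PPS2, a subject who leaves after Visit 4 stays in the set. Its nesting in PPS1 adds a Visit 2 condition, but Visit 2 precedes Visit 4. The Stage 2 half of the point therefore rests on the SAP wording alone.

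**Inputs for size**

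The plan randomizes 300 + 20 = 320, which reproduces its figure. The allowance is 20/320 = 6.25% for the whole study. If all of it fell between Visits 1 and 2, that is 10 per arm of 160. If all of it fell between Visits 4 and 5, it is 5 per arm of 80. These are alternatives; the two cannot both happen within the allowance.

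The trial's assumed rates are blacked out. As assumptions I use the Phase 2 rates in protocol 3.2: 30.1% against 13.5% for Nyxol alone, and 60.45% against 27.9% for the combination. They come from other times and conditions than Visits 1 and 4, so they give scale only.

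**Formula**

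PP rate = (n·p − d·q)/(n − d), where n is the arm size, p the rate in all subjects, d the number who leave, and q the rate among them. Typical means q = p.

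*Visit 1, n = 160, d = 10 per arm; difference in all subjects 16.6 points*

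| Leavers | PP rates | Difference | Shift |
|---|---|---|---|
| Typical in both arms | 30.1 v 13.5 | 16.6 | 0 |
| Non-responders on Nyxol, typical on placebo | 48.16/150 = 32.1 v 13.5 | 18.6 | +2.0 |
| Non-responders in both arms | 32.1 v 21.6/150 = 14.4 | 17.7 | +1.1 |
| Typical on Nyxol, non-responders on placebo | 30.1 v 14.4 | 15.7 | −0.9 |

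*Visit 4, n = 80, d = 5 per arm; difference in all subjects 32.55 points*

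| Leavers | PP rates | Difference | Shift |
|---|---|---|---|
| Typical in both arms | 60.45 v 27.9 | 32.55 | 0 |
| Non-responders on active, typical on placebo | 48.36/75 = 64.5 v 27.9 | 36.6 | +4.0 |
| Non-responders in both arms | 64.5 v 22.32/75 = 29.8 | 34.7 | +2.2 |
| Typical on active, non-responders on placebo | 60.45 v 29.8 | 30.7 | −1.9 |
| 80% responders on active, typical on placebo | (48.36 − 4)/75 = 59.1 v 27.9 | 31.2 | −1.3 |

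The last row stands for subjects who respond but do not tolerate the drops.

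**A smaller dropout**

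In Phase 2 one combination subject of about 44 (15/0.341) withdrew for adverse events, which scales to about 2 of 80. Two non-responders leaving the active arm, and none the comparator, give 48.36/78 = 62.0 against 27.9: a difference of 34.1 and a shift of +1.55. That study was shorter, so this is only a guide.

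**The case against.** The strongest reply is that mITT analyses of the same endpoints are stated in several places. Protocol 5.1 assigns all efficacy endpoints to mITT and only selected ones to PP; protocol 10.3.5 names both sets for the continuous and the responder analyses; SAP 7.1.1 and the opening of SAP 9 also name mITT. SAP 7.1.2 and 7.1.3 limit the PP sets to select endpoints, and the table list that settles the matter is blacked out. A reader might infer from SAP 9.1.2 that every Visit 1 and Visit 4 result is run in PP only. The visible text does not show that. What stands is that SAP 9.1.2 reverses the protocol's order of the two sets, and that a parallel mITT table would not mend the PP one.

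A reader might also take the problem to exist whichever PPS2 definition is adopted. That holds for Visit 1 but not for Visit 4.

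It may also be said that one set per stage, with stable denominators, is a common supportive choice. That is fair for endpoints at Visits 2 and 5. It does not justify discarding valid earlier readings.

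The early-termination rule in SAP 7.3.3 could place a leaver's reading at Visit 2 or 5, but the dosing conditions would still keep out a subject who had stopped treatment.

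**Conclusion.** The point holds for PP analyses of secondary endpoints: at Visit 1 under both documents, and at Visit 4 under the SAP's PPS2 only. The primary endpoint is not affected. Under SAP 7.4.1, secondary p-values outside the testing hierarchy are descriptive, and the comparisons that SAP 7.5 names are all at Visit 5, although the full hierarchy is blacked out.

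The shift is zero if leaving is unrelated to response. Where it is related, the cases above give about 1 to 4 points in favour of active treatment, or about 1 to 2 points against it. These figures rest on Phase 2 rates and on spending the whole allowance in one interval.

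Two stronger readings are tempting. One is that the sets favour whichever arm has more treatment-related dropout. The documents do not support this: intolerance is not non-response, and placebo subjects may leave for lack of benefit. The other is a larger bias. Ten non-responders lost from the combination arm alone would give 48.36/70 = 69.1 against 27.9, a shift of about 8.6 points, but nothing in the documents suggests so one-sided a loss.

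**What to change.** - Make mITT the main set for Visit 1 and Visit 4 secondary endpoints, in line with protocol 5.1. With observed cases, this keeps every treated subject who has a baseline value and a reading at that time.
- Define any PP set for those visits by dosing, readings and deviations up to the visit analysed. For Visit 1: baseline readings, the in-office Treatment 1 drop, and the reading at that time point. For Visit 4: Treatment 1 the evening before, Treatment 2 at the visit, and the reading at that time point.
- Apply the Visit 2 and Visit 5 conditions only to endpoints at those visits.
- Reconcile the PPS2 definition between protocol 10.2 and SAP 7.1.3, and list the change in SAP 3.3, which at present states that the SAP's analyses are consistent with the protocol.

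The cost is SAP wording and two population flags, to be settled before unmasking. The downside is that PP sample sizes will differ by visit, which table footnotes can explain.

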#### **7.1.3. Per Protocol Stage 2 Population (PPS2)**

The PP Stage 2 (PPS2) Population will include all subjects in the mITT Population who receive 1 drop of Treatment 1 the day prior to Visit 4 and Visit 5, receive 1 drop of Treatment 2 (LDP or LDP vehicle) at Visit 4 and Visit 5, have binocular DCNVA and BCDVA in photopic conditions at the 30 Minute timepoint at Visit 5 (after Treatment 2 dosing), and have no major protocol deviations considered to have significant impact on treatment outcome in Stage 2. The PPS2 Population will be used for analysis of select efficacy endpoints.

#### **7.1.4. All Randomized Population (ARP)**

The ARP will include all randomized subjects. This population is also known as the Intention-to-Treat (ITT) Population. The ARP will be used in confirmatory efficacy analyses, with subjects included in their randomized treatment regardless of the treatment they actually received.

#### **7.1.5. Safety Population (SP)**

The SP will include all randomized subjects who have received at least 1 drop of study treatment (Treatment 1 or Treatment 2). The SP will be used to summarize safety variables, using the actual treatment a subject received.

## **7.2. Covariates and Subgroups**

### **7.2.1. Planned Covariates**

Planned covariates include baseline values for the given assessment.

### **7.2.2. Planned Subgroups**

Subgroup analyses [REDACTED]

## **7.3. Management of Analysis Data**

### **7.3.1. Data Handling**

Data from unscheduled visits may be used for the primary efficacy analysis as described in Section 7.3.2.3 below. Otherwise, unscheduled visit data will not be included in the analysis of efficacy or safety but will be listed.

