#### 8.2.6. Unscheduled Visits

An unscheduled visit may be any visit to the Investigator other than the specific visits requested in the protocol as possibly required for the subject's ophthalmic condition. The Investigator will perform all procedures necessary to evaluate the subject at these visits and record any AEs in the eCRF.

As noted in Section 5.9.4, every possible effort should be made by Investigators to assure that subjects who discontinue early from the study have a telephone follow-up that includes assessments of AEs and concomitant medications.

09/29/2023 Page 44 of 76

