#### 9.3.1. Adverse Event Definitions

The following definitions of terms apply to this section:

*Adverse event*. An AE is any untoward medical occurrence associated with the use of a study medication in humans, whether or not it is considered drug related. An AE can therefore be any unfavorable and unintended sign (including abnormal laboratory findings), symptom, or disease temporally associated with the use of the study medication, whether or not related to the study medication. Study medication includes the investigational drug under evaluation and the comparator product or vehicle placebo that is given or administered during any phase of the study.

Medical conditions/diseases present before starting the investigational treatment are only considered AEs if they worsen after starting the investigational treatment. Abnormal test results constitute AEs only if they induce clinical signs or symptoms, are considered clinically significant, or require therapy.

The occurrence of AEs should be sought by open-ended questioning of the subject at each visit during the study. At each clinic assessment/visit, study personnel should ask the following question: "Have you had any problems since your last assessment/visit?" Adverse events also may be detected when they are volunteered by the subject during or between visits or through study assessments.

*Life-threatening adverse event or life-threatening suspected adverse reaction*. An AE or suspected adverse reaction is considered "life-threatening" if, in the view of either the Investigator or Ocuphire, its occurrence places the subject at immediate risk of death. It does not include an AE or suspected adverse reaction that, had it occurred in a more severe form, might have caused death.

*Serious adverse event or serious suspected adverse reaction*. An AE or suspected adverse reaction is considered "serious" if, in the view of either the Investigator or Ocuphire, it results in any of the following outcomes:

- Death
- Life-threatening AE
- Inpatient hospitalization or prolongation of existing hospitalization
- Persistent or significant incapacity or substantial disruption of the ability to conduct normal life functions
- Congenital anomaly/birth defect
- Other medically important serious event

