## **10. SAFETY ANALYSES**

All safety analyses will be conducted using the SP unless specified otherwise below. All safety analyses will be completed using the actual treatment a subject received. Observed case data will be used; no imputation will be performed for missing safety data except for the limited situations described in Section 7.3.2.

All safety data will be presented in by-subject listings. Unscheduled assessments will not be summarized but will be included in the listings.

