### **10.1. Adverse Events**

AEs will be coded using MedDRA, Version 25.1.

Treatment-emergent adverse events (TEAEs) are defined as any AE that begins or worsens after initiation of the investigational product and through the subject's last study visit (study completion or early termination).

If the onset of an AE is on or after the date of first dose of study medication or is increasing in severity after first dose of study medication, then the AE will be considered treatment emergent.

Only TEAEs will be summarized; all AEs (TEAE, non-TEAE) will be included in a by-subject listing.

TEAEs that start during Stage 1 will only be counted in the Stage 1 tables using the Treatment 1 that was actually taken, regardless of the TEAE stop date. TEAEs that start during Stage 2 will be counted in both Stage 1 and Stage 2 tables.

The number and percent of subjects with any TEAEs will be summarized by SOC and PT by treatment group and overall. At each level of tabulation (e.g., at the PT level), subjects will be counted only once if they had more than one such event reported during the AE collection period.

Note that in MedDRA, ocular events are coded to the SOC of "Eye Disorders". Thus, using SOC in the summaries will provide a separation of ocular and non-ocular adverse events.

The following summary tables will be presented for TEAE data:

- Overall summary of TEAEs (completed for both the SP and mITT population)
- Summary table of TEAEs by SOC and PT
- Summary table of TEAEs by SOC, PT, and by greatest relationship level to study drug (not related, unlikely related, possibly related, probably related, definitely related, or unknown)
- Summary table of TEAEs by SOC, PT, and maximum severity (mild, moderate, severe)

- Summary table of serious TEAEs by SOC and PT
- Summary table of TEAEs leading to withdrawal from the study by SOC and PT
  
- Summary table of TEAEs leading to study medication discontinuation by SOC and PT

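### IOP, acuity, slit-lamp, fundus and vital-sign results from unscheduled visits are listed only, unless they become an AE or early-termination data; a by-arm worst-value summary would close the gap

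*SAP*

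**What the plan says.** SAP 7.3.1 opens with an allowance: "Data from unscheduled visits may be used for the primary efficacy analysis as described in Section 7.3.2.3 below". It then closes the door on everything else: "Otherwise, unscheduled visit data will not be included in the analysis of efficacy or safety but will be listed". SAP 10 restates this for safety: "Unscheduled assessments will not be summarized but will be included in the listings".

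Protocol 8.2.6 describes an unscheduled visit as any extra visit that the subject's eye condition may call for, and adds: "The Investigator will perform all procedures necessary to evaluate the subject at these visits and record any AEs in the eCRF".

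SAP 10.4, 10.5 and 10.7 summarise vital signs, IOP, biomicroscopy and ophthalmoscopy at baseline, at Visit 2 (12 h after Treatment 1) and at Visit 5 (8 h). SAP 10.8 places BCDVA loss of 5 or more letters inside a secondary efficacy summary. The readable text describes no summary of worst post-baseline values.

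**The concern.** A subject who comes in between planned visits may well do so because of an eye problem, so readings taken then are more likely than scheduled ones to show trouble. If they are left out of the by-arm summaries, those summaries lean towards no change.

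The planned tables have little to set against this. In Stage 2, the only stage with pilocarpine, pressure, slit-lamp, fundus and vital signs are looked at once, 8 hours after the in-office drop. Table 4 in Protocol 5.4.1 says pilocarpine may raise IOP temporarily before lowering it, and Protocol 3.1 reports peak pupil effect at 30 to 60 min. Protocol 3.2 names angle-closure and retinal-detachment risks for the approved pilocarpine product. SAP 7.4.2 plans no safety monitoring committee, so the final by-arm tables carry the safety comparison.

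**Working it through.** The plan states no figure on this point, so the check is mainly a comparison of sections, with simple counts.

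**1. Scheduled looks after baseline**
- IOP, biomicroscopy, ophthalmoscopy, HR/BP (SAP 10.4, 10.5, 10.7): Visit 2 at 12 h and Visit 5 at 8 h. That is 2 looks, of which 1 is in Stage 2. The Stage 2 schedule (Protocol Table 2) shows none of these at Visit 4.
- Efficacy time points (SAP 9.1): Visit 1 has 5 post-dose, Visit 2 has 6, Visit 3 has 1, Visit 4 has 6 and Visit 5 has 6. 5 + 6 + 1 + 6 + 6 = 24. BCDVA loss is reported with these. The BCDVA rows of the schedule are not visible, so 24 is the number of efficacy time points, not a confirmed number of BCDVA readings.
- Distance between the two sparse looks: Visit 2 is Day 8 and Visit 5 is Day 22 to 29 (Protocol 5.5). 22 − 8 = 14 and 29 − 8 = 21, so 14 to 21 days, of which 7 to 14 are off-drug washout.

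**2. Routes from an unscheduled visit to a by-arm table**
- *Direct summary of the reading:* closed by SAP 7.3.1 and 10.
- *Adverse event:* open. The investigator must record AEs found at the visit (Protocol 8.2.6). Protocol 9.3.1 also says: "Adverse events also may be detected when they are volunteered by the subject during or between visits or through study assessments". SAP 10.1 decides treatment emergence by timing ("If the onset of an AE is on or after the date of first dose of study medication", or worsening after it), not by visit type, and then: "The number and percent of subjects with any TEAEs will be summarized by SOC and PT by treatment group and overall".
- *Early termination:* open for subjects who leave. SAP 7.3.3 assigns their data to a nearby scheduled visit or time point.

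**3. What neither open route carries**
- Protocol 9.3.1 limits when a result is an AE: "Abnormal test results constitute AEs only if they induce clinical signs or symptoms, are considered clinically significant, or require therapy". An IOP rise or new slit-lamp finding judged to meet none of these conditions stays in a listing.
- When an AE is recorded, the tables show preferred term, severity and relationship. The change in mmHg or letters is not shown.
- Early-termination mapping does nothing for a subject who came in and stayed on study.

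**4. Per-subject sensitivity**
Arm sizes are the approximate numbers in Protocol 5.
- Stage 2 arm: 1/80 = 1.25 percentage points.
- Stage 1 group: 1/160 = 0.625, about 0.6 percentage points.

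These show how far one subject moves a proportion. They are not an expected event rate; the documents give no rate of unscheduled visits or of findings at them.

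**The case against.** The strongest reply is that anything clinically important already has a route. A new complaint that brings a subject in fits the protocol's AE definition, and a finding that is symptomatic, clinically significant or treated must be recorded. It then appears by arm in the treatment-emergent AE tables. This stands. A reader might infer from SAP 7.3.1 that unscheduled findings are shut out of every safety analysis, or are invisible by arm. The documents do not support that. Read literally, the phrase about unscheduled visit data could take in AEs, but SAP 10 speaks of assessments and SAP 10.1 sets no condition on visit type, so the consistent reading keeps AEs in. What is lost is the measured value, and findings not judged to be AEs.

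A reader might also infer that the SAP is lenient towards efficacy and strict towards safety, because unscheduled data may enter the primary analysis. That cannot be shown. The text of SAP 7.3.2.3 is not visible, so it is unknown when such values are used or which way they count, and other efficacy analyses exclude them too.

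Three further points stand. Acuity does not share the two-look limit. Protocol 8.2.6 says only that such a visit is possibly required for the eye condition, so enrichment for problems is likely but not stated. Keeping irregular readings out of by-visit means is sensible.

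The planned-table list is redacted, so an extra table cannot be ruled out, although SAP 10 makes one that uses unscheduled values unlikely.

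**Conclusion.** The gap is real and modest. By rule, unscheduled IOP, BCDVA, biomicroscopy, ophthalmoscopy and HR/BP results are listed only. They enter by-arm tables only through an AE record, which drops the size of the change, or through early-termination mapping. The effect is greatest for the measures with two post-baseline looks and one in Stage 2, and smaller for BCDVA.

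Its size in this trial cannot be estimated from the documents; each subject affected counts for 1.25 points of a Stage 2 arm or about 0.6 points of a Stage 1 group. The conclusion assumes that some unscheduled visits occur with these measurements taken, and that no redacted table already covers them. It is a worthwhile, inexpensive improvement and does not call the primary result into question.

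**What to change.** - Leave unscheduled data out of the by-visit summaries, as planned.
- Add a descriptive by-arm summary of the worst post-baseline result, from scheduled or unscheduled visits: largest IOP rise, any BCDVA loss of 5 or more letters, any new or worsened slit-lamp or fundus finding, and the most extreme HR and BP change.
- Assign each result to Stage 1 or Stage 2 by date. Name the cut date, because Protocol 8.2.2 ends Stage 1 after the washout and 8.2.3 ends it at Visit 3.
- Amend SAP 7.3.1 and 10 to allow this summary, and say in 7.3.1 that AEs are tabulated whatever the visit type.

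**Cost.** SAP wording and a few table rows, from data already collected. More extreme values will appear in the safety tables. A subject with more readings also has more chances of an extreme one, so show the number of subjects with unscheduled visits by arm beside the summary. If the data are already unmasked, SAP 3.2 allows the analysis to be reported as post hoc.
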